[name] will be the non-blind PI and will primarily be responsible for supervision of the interventionists and ensuring therapist/ yoga instructor adherence. [name] will be the blind PI and will be primarily responsible for the supervision of the research assistants. [name], the study statistician, will be blind to group assignment (and will have no contact with participants.) When there is a question about whether a participant meets inclusion criteria, [name] will make a decision about inclusion. Drs. [name], [name], and study RAs will meet separately to discuss intervention-specific concerns (e.g., need to cancel class due to lack of participants).

To ensure that blindness will be maintained, there will be a separate data collection instrument in REDCap to enter randomization assignment. Only non-blind study personnel will have access to this section of REDCap. We will also have a separate section in REDCap for intervention specific data (e.g., dates of sessions attended, yoga homework) that only the non-blinded staff will have access to.

In reporting adverse events to the Safety Monitoring Committee, determination of “causal relationship” will be made by the non-blind PI only, as it may require knowledge of which intervention arm the participant is in. The standard Adverse Events Reporting Form of our IRB does not ask for intervention arm; thus risk of unblinding from AE reporting is minimal.

The non-blind PI will meet with yoga instructors and HE instructors for supervision. The instructor/ therapist adherence ratings will be conducted by the non-blind PI and RA.

We will keep a record of any instances of unblinding. This record will be used to improve procedures for a larger clinical trial. After all data are collected and the database is locked, the blind PI may be unblinded so as to contribute to data interpretation.

Participants cannot be blind to study intervention. However, we will present both interventions (Yoga or HE) with equipoise to all participants in written materials and orally.

6.2.6 Follow-up Visits - Phase 2.

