Although group discussion will be kept to a minimum in the yoga class, a participant's confidential statements during any of the study group sessions (e.g., focus group, yoga class, health education group) may be disclosed by another member of their corresponding group. To minimize risk, we will remind all participants that: a) any group discussion should be kept confidential; and b) because we cannot guarantee confidentiality due to the group nature of the discussion, all participants should be careful about disclosing anything that they want kept private. Finally, we will ask all participants not to disclose the names of prisoners in their group to others outside the group.

5. We will minimize potential risk for physical injury by: a) requiring all participants in yoga classes to be medically appropriate for moderate physical activity; and b) requiring all instructors to be registered yoga teachers with experience in directing people in how to achieve yoga postures without physical injury. Class content will be designed to accommodate the needs of yoga-naïve students who are not currently physically active. By presenting modifications of all postures, and by using props (e.g., chairs, blankets), the risk for injury will be minimized. Injuries due to yoga will be monitored at frequent intervals during this part of the study and patients will be followed for a sufficient period of time (2 months) after completing yoga classes to ensure stabilization of injuries.

Benefits of the proposed research to the subjects and others.

The potential risks associated with participation in this study appear to be mild to moderate. Although there is a risk for distress, the procedures proposed for monitoring distress should ensure that participants who require a higher level of care receive it. Participants assigned to yoga may benefit from improved anger regulation and associated behaviors. The study provides additional screening, assessment, and referral to emergency services, as needed, for all study participants, and in no way restricts or limits the treatment individuals would have received had they not participated in the study. Moreover, participants are helping other incarcerated individuals with high levels of anger dysregulation by providing information that will improve treatments for this population. Thus, the potential benefits outweigh the potential risks of the study.

Importance of knowledge to be gained.

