7.2 Specification of Safety Parameters

Safety issues will be minimal in Phase 1 given that participation involves only a single focus group, no yoga classes, and no formal assessment of suicidality. However, should an issue arise (e.g., a voluntary report of suicide ideation), staff would manage it in the same way that they would manage it in Phase 2.

Please see Table 4 for a summary of safety issues, how they are assessed, when they are assessed, and relevant staff actions.

Table 4. Assessment and Management of Safety Issues, Summary, Phase 2

Safety Issue	How assessed	When Assessed in Phase 2	Relevant Research Staff Actions
Suicide or homicidal ideation	PHQ-9 Participant report to research staff	BL, wk5, wk10, wk18 Any point	Immediate clinical assessment as described in DSMP
Injuries due to yoga	Structured self-report	Weekly during first 10 weeks	Follow until resolution; may result in changes to yoga instructor manual
Other AEs	SAFTEE Participant report to research staff	BL, wk5, wk10, wk18 Any point	If related to study participation, follow resolution; potential changes to procedures particularly if AE is also unexpected

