Unanticipated problems will be recorded in the data collection system throughout the study. Study staff will record all reportable events with start dates occurring any time after informed consent is obtained until 8 weeks (i.e., follow-up assessment after the last day of class participation). Each time participants attend classes, we will inquire about injuries due to study participation. At midpoint, endpoint, and at week 8 follow-up, study staff will administer the SAFTEE in order to inquire about the occurrence of AE/SAEs during the previous 8-10 weeks. SAEs related study participation will be followed for outcome information until resolution or stabilization.

Characteristics of an adverse event will include: a) relationship to study intervention, b) expectedness of SAEs, and c) event severity.

Relationship to Study Intervention

To assess relationship of an event to study intervention, the following guidelines are used:

1. Related (Possible, Probable, Definite)
 - a. The event is known to occur with the study intervention.
 - b. There is a temporal relationship between the intervention and event onset.
 - c. The event abates when the intervention is discontinued.
 - d. The event reappears upon a re-challenge with the intervention.
2. Not Related (Unlikely, Not Related)
 - a. There is no temporal relationship between the intervention and event onset.
 - b. An alternate etiology has been established.

Relatedness of SAEs

The Study PI and Independent Monitoring Committee will be responsible for determining whether an SAE is expected or unexpected. An adverse event will be considered unexpected if the nature, severity, or frequency of the event is not consistent with the risk information previously described for the intervention. The risk information to assess expectedness can be obtained from preclinical studies, the investigator's brochure, published medical literature, the protocol, or the informed consent document.

Expected AEs for this study include:

- Any event that may be reasonably anticipated to occur as a result of the study procedure (i.e., mild aches or pains following a yoga class)

Severity of Event

The following scale will be used to grade adverse events:

1. Mild: no intervention required; no impact on activities of daily living (ADL)
2. Moderate: minimal, local, or non-invasive intervention indicated; moderate impact on ADL

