Acceptability and Feasibility. Intervention credibility and patient expectations for intervention success at baseline will be measured with the Credibility Expectancy Questionnaire (CEQ)²³; this is administered after their initial class. The Client Satisfaction Questionnaire (CSQ-8)²⁴ will be used post-treatment to assess satisfaction with treatment. We will also use qualitative responses to a detailed post-treatment interview to gain participants' feedback about intervention components and research procedures. Finally, it is critical that the amount of yoga practice at home be measured as accurately as possible. Participants will complete a yoga homework questionnaire on a weekly basis. The tool will yield three indices of home practice: frequency of extended home practice, minutes of extended home practice, and frequency of micro home practice.

Participant safety. After each homework questionnaire, we will ask participants in the yoga arm only whether they experienced any injuries as a result of yoga practice. At each follow-up, we will administer the Systematic Assessment of Treatment-Emergent Events – General Inquiry (SAFTEE)²⁵ to all participants. This allows us to systematically assess number of adverse events, severity, and resulting impairment. Finally, any time a participant reports an adverse event to any staff member, a research assistant will talk with the participant to ascertain information for recording of the adverse event. For adverse events ascertained by any of these three possible methods, the research assistant gets information on what happened, start and stop dates, severity, functional impact, interactions with healthcare professionals, perceived cause, and possible relation to study participation. For more information and details on coding of AEs, please see DSMP.

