9.5 Outcomes

9.5.1 Primary Outcome.

The primary outcomes are acceptability, feasibility, and safety.

Target treatment development outcomes. We monitor treatment development outcomes (see Table 6) throughout the trial. Target outcomes were chosen on face validity, clinical experience, and, when available, relevant clinical literature. At 3 time points throughout the RCT (i.e., after enrolling 10, 20, and 40 participants), the scientific team will convene to discuss how our actual procedural outcomes compare to the target outcomes. Discrepancies will result in: 1) investigation (using qualitative or other data) of the reason for the failure to meet this outcome; and 2) discussion amongst the research team. Depending on the nature of the discrepancy, we may modify recruitment procedures, assessment procedures, instructions to participants, instructor training procedures, or other aspects of the trial. Ultimately, failure to meet these outcomes could result in a decision not to write a grant proposal for a large-scale RCT; in other cases, it may inform the design of a subsequent RCT.

Primary data analyses will be focused on feasibility and acceptability (see Table 6) using intent-to-treat population. Study measures and endpoints will continue to be collected for all enrolled participants if they are willing, even in the event of premature discontinuation of the study intervention.

Table 2. Target Outcomes

Description (Assessment method)	Target
Feasibility and Acceptability-- Hatha yoga, Health education	
Acceptability (qualitative interview)	Most feedback positive; few substantive negative comments. Negative comments used to enhance procedures.
Credibility at baseline (CEQ)	Average > 50 (i.e., midpoint score between low and high credibility) on subscale
Expectancy at baseline (CEQ)	Average > 50 (i.e., midpoint score) on subscale
Program satisfaction (CSQ-8)	Average total score > 24
Home practice (homework questionnaire)	70% of yoga participants engage in practice at least 2 times per week for 6/10 weeks.
Class attendance	70% of all participants complete 6/10 classes in the RCT
Instructor adherence (Adherence measures)	Yoga instructors and HE instructors achieve at least 80% adherence on a random subset of classes taught
Class size	70% of classes have 4 or more participants.
Safety	
Adverse events (SAFTEE; injuries due to yoga)	No serious adverse events or injuries that are possibly, probably, or definitely related to study participation.

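### The frequent injury check is described as asking only about injuries the participant already attributes to yoga or the study, so other injuries are less likely to be captured for the primary safety target

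*Combined protocol and SAP*

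**What the plan says.** **The recurring check.** Section 9.1.2 comes closest to giving the question itself: after each homework questionnaire, "we will ask participants in the yoga arm only whether they experienced any injuries as a result of yoga practice". Section 7.4 puts it differently: "Each time participants attend classes, we will inquire about injuries due to study participation". DSMP section 3.2 repeats the section 7.4 text. Table 3 (section 6.1), Table 4 (section 7.2) and the target-outcomes table in section 9.5.1 name the measure as injuries due to yoga. Table 4 gives the method as "Structured self-report". Section 7.1 states in general terms that "Injuries due to yoga will be monitored at frequent intervals during this part of the study", and DSMP section 5 repeats it. No section describes a cause-neutral version of this check.

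**What the plan does with cause.** Section 7.4 defines an adverse event without regard to its relationship to the study. It grades relatedness on features such as timing and alternative cause. Section 6.2.5 says that, in adverse event reports to the Safety Monitoring Committee, the causal determination "will be made by the non-blind PI only". The safety target in section 9.5.1 is "No serious adverse events or injuries that are possibly, probably, or definitely related to study participation".

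**Other capture routes.** SAFTEE, a general inquiry, goes to all participants at weeks 5, 10 and 18 after baseline (Table 3, section 9.1.2). Any event may be reported to any staff member at any time (section 9.1.2, Table 4). Yoga instructors watch for physical injury of any kind during each class (section 7.1). For events found by the frequent item, SAFTEE or participant report, the research assistant records perceived cause and possible relation to the study (section 9.1.2).

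**The concern.** A question about injuries resulting from yoga asks the participant to settle the cause before anything is written down. Someone whose back hurts two days after class, and who blames the bunk or a work detail, can truthfully answer no. The frequent item then yields nothing to rate. Uncertain cases of this kind are what the possible grade exists for.

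Mild physical injury is the only adverse event that section 7.1 expects from yoga. Safety is a primary outcome, and section 9.5.1 says that missed targets could lead to a decision not to propose the large trial. A target of zero related injuries becomes easier to meet when fewer injuries are recorded, so reduced capture errs in the reassuring direction.

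**Working it through.** The plan gives no injury rate and no capture rate, so there is no figure of its own to reproduce. The check has two parts.

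**1. The routes compared**

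| Route | Who and when | Conditioned on cause? | Limit |
|---|---|---|---|
| Injury item | After each class (Table 3) or weekly for 10 weeks (Table 4); yoga arm only (9.1.2) or no arm stated (7.4, DSMP 3.2) | Yes, in every description | Misses unattributed injuries |
| SAFTEE | All participants, weeks 5, 10 and 18 | No | Gaps of 5, 5 and 8 weeks; depends on attendance (retention targets 80% at week 10, 70% at week 18) |
| Volunteered report | Anyone, any time | No | Participant must raise it |
| Instructor observation | Yoga classes | No | Cannot see pain that starts later, or injury in the between-class practice assigned under 5.2.1 |

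The target-outcomes table names only the first two as the measures for the safety target. The injury item is the only frequent self-report among the four.

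**2. Illustrative size**

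Inputs:
- n = 20 in yoga: half of 40, from the 1:1 allocation in DSMP section 7.2.
- p = risk that a yoga participant has an injury the PI would rate at least possibly related. Assumed, 5% or 10%.
- s = share of such injuries that the participant attributes to yoga and so reports on the item. Assumed, 75% or 50%.
- c = share of the remainder recovered by the other routes. Assumed, 0, 50% or 80%.

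Participants are treated as independent, with at most one such injury each.

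Overall capture: e = s + (1 - s)c. Chance of recording no injury: (1 - p·e)^20.

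For p = 10% and s = 50%:
- full capture, e = 1: 0.90^20 = 0.122
- c = 0, e = 0.50: 0.95^20 = 0.358
- c = 50%, e = 0.75: 0.925^20 = 0.210
- c = 80%, e = 0.90: 0.91^20 = 0.152

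| p | s | Full capture | c = 0 | c = 50% | c = 80% |
|---|---|---|---|---|---|
| 10% | 75% | 12% | 21% | 16% | 14% |
| 10% | 50% | 12% | 36% | 21% | 15% |
| 5% | 75% | 36% | 47% | 41% | 38% |
| 5% | 50% | 36% | 60% | 47% | 40% |

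The same loss affects how a zero count is read. With complete capture, 0 of 20 gives a one-sided 95% upper bound of 1 - 0.05^(1/20) = 13.9%. Dividing by e gives the bound on the true risk: 13.9/0.75 = 18.5% at e = 0.75, and 13.9/0.90 = 15.5% at e = 0.90.

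**The case against.** A reader might infer that possibly related injuries are filtered out before the PI can rate them. The documents do not support that. SAFTEE and volunteered reports are cause-neutral, instructors look for any injury in class, and SAFTEE is one of the two named measures behind the target. Section 7.4 gives SAFTEE an 8-10 week look-back, which covers every gap between visits. The column with c = 0 is therefore a worst case, not an estimate.

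A reader might also infer that the participant takes over the PI's causal decision. Section 6.2.5 concerns reports to the committee. An answer to a screening item is not that determination, and section 9.1.2 treats perceived cause as one data item among several. The two sections do not contradict each other. What remains is narrower: on this item, the participant's view of cause decides whether there is a record at all.

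The form itself is not reproduced, so its wording is inferred from descriptions. Some of these are only labels, and the section 7.1 sentence is a general statement about monitoring. The actual form may probe more openly. Still, both sections that paraphrase the inquiry, 9.1.2 and 7.4, condition it on cause.

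Finally, an any-cause question put to the yoga arm alone would collect background aches in one arm only. That objection is sound and shapes the fix.

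**Conclusion.** The point holds as one of reduced capture. Followed as written, the frequent item misses injuries that the participant does not attribute to yoga or the study. Those injuries depend on less frequent recall, on volunteering, or on being seen in class. They can still reach the PI and be rated.

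At an assumed 10% risk with half of injuries attributed, the chance of recording none rises from 12% to about 15-21% when the other routes recover 50-80% of the missed injuries, with 36% as the limit if they recover nothing. None of p, s or c is in the documents, and the loss is smaller if more injuries are attributed. This is not a flaw that invalidates the safety assessment. It is an inexpensive improvement to a primary outcome measure and should be made.

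**What to change.** - Reword the item in sections 9.1.2 and 7.4 and in DSMP section 3.2 to ask about any new injury or physical pain since the participant was last asked, whatever the cause. Relabel it in Tables 3 and 4, and bring section 7.1, DSMP section 5 and the target-outcomes table into line.
- Ask it in both arms, so that any-cause events are collected evenly. This also reconciles the yoga-only wording in section 9.1.2 with the unrestricted wording in section 7.4 and DSMP section 3.2.
- Reconcile the timing: after each class in Table 3, weekly in Table 4. Under the first, someone who stops attending may not be asked.
- Keep perceived cause as the separate field that section 9.1.2 already provides. Have the non-blind PI rate every recorded injury on the section 7.4 scale, and keep the safety target on PI-rated relatedness.

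The cost is one reworded question and more unrelated aches to log and rate. No visit or staff is added: section 6.2.6 already describes a brief assessment after each class attended, without an arm limit.

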7.2 Specification of Safety Parameters

Safety issues will be minimal in Phase 1 given that participation involves only a single focus group, no yoga classes, and no formal assessment of suicidality. However, should an issue arise (e.g., a voluntary report of suicide ideation), staff would manage it in the same way that they would manage it in Phase 2.

Please see Table 4 for a summary of safety issues, how they are assessed, when they are assessed, and relevant staff actions.

Table 4. Assessment and Management of Safety Issues, Summary, Phase 2

Safety Issue	How assessed	When Assessed in Phase 2	Relevant Research Staff Actions
Suicide or homicidal ideation	PHQ-9 Participant report to research staff	BL, wk5, wk10, wk18 Any point	Immediate clinical assessment as described in DSMP
Injuries due to yoga	Structured self-report	Weekly during first 10 weeks	Follow until resolution; may result in changes to yoga instructor manual
Other AEs	SAFTEE Participant report to research staff	BL, wk5, wk10, wk18 Any point	If related to study participation, follow resolution; potential changes to procedures particularly if AE is also unexpected

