5.2 Handling of Study Interventions

5.2.1. Hatha Yoga Intervention.

The yoga intervention will involve an initial individual session with a yoga teacher, designed to increase motivation for yoga class attendance and self-efficacy for adapted yoga practice (see below) between classes. Following the initial individual session, participants will be invited to attend one 60-75 minute yoga class for 10 weeks in the prison facility where they reside. Each class will consist of: breathing exercises, brief guided centering meditation, warm-ups, standing postures, floor postures, an inversion, relaxation, and between-class practice assignments. Classes will emphasize mindfulness, including noticing emotions, thoughts, and physical sensations related to anger, and moderate physical activity. Classes will include some teaching of a relevant yoga theme, such as nonviolence (ahimsa). We will plan themes with input from prisoners and other stakeholders prior to starting classes and rotate through themes. Themes may be introduced via a brief meditation at the beginning of class, and mentioned briefly through class. Between-class practice assignments will be tailored to the prison setting. With input from our stakeholders, we will design a series of brief yoga practices that prisoners can engage in either a) on a daily basis, such as when they wake up or before bed; and b) when they notice that they need to cope with angry or other difficult feelings. Practices may include breathing exercises, brief meditation, and simple poses. We will provide participants with written descriptions and diagrams to assist them with yoga practice. Because each participant will have an individual introduction session with a yoga teacher before beginning the classes, and because sessions are not cumulative, participants can

enter the group at any time (i.e., rolling enrollment). Minimum class size is 1, maximum is 10. We prefer to have a group of at least 4 participants for a group effect, with larger groups (i.e. 8-10) being more cost-effective, of 8-10, but recognize that there will be times that not all participants can attend; thus, we will run the classes as long as 1 participant attends.

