For all follow-up assessments, research staff will make every effort to conduct the assessment within one week before or one week after the exact due date of the assessment. However, because all data can be analyzed with modern statistical methods regardless of whether it was collected inside that window, RAs will still collect data if possible even if it is later than that two-week window. We will record optimum date for the assessment as well as the actual date of the assessment.

Participants will complete a brief assessment after each class that they attend.

In addition, all participants will be assessed at: baseline, 5 weeks (mid-intervention), 10 weeks (post-intervention), 14 weeks (yoga group participants only), and at 8 week follow-up. In addition to demographics, we will assess acceptability of the intervention conditions, safety of the yoga condition, anger and aggression, secondary outcomes (depression and anxiety symptoms, general functioning), potential intervention mechanisms of action (anger rumination, decentering, impulsivity), and other descriptive characteristics (trauma history, treatment utilization, physical activity levels).

In the event that a participant is released back into the community before they complete all of their study assessments, we will complete them in the community. We will aim to complete all of these follow-up assessments by telephone. However, there may be some circumstances that might make it difficult for a participant to complete the follow-up assessment by telephone (e.g., limited phone minutes, enrollment in a residential treatment program). In such cases, we will complete the follow-up assessment in person in our offices at Brown University or in the facility where the participant is located (e.g., residential treatment facility, with facility approval). Additionally, if a participant is transferred to another facility at RIDOC, we will complete their assessments at the other facility (e.g., Men's Maximum Security) with RIDOC approval.

Please see table 3 for a list of all assessments to be completed at each visit.

6.2.7 Completion/Final Evaluation - Phase 2

Even if prisoners drop out of study treatment, we will attempt to collect data at all assessment points if prisoners agree to it.

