8. INTERVENTION DISCONTINUATION

Prisoners will be discontinued from an intervention in the following circumstances:

- If the prisoner or prison staff does not believe it is in the best interest of the prisoner to continue. As soon as an MPI is informed of this, study staff will speak with the participant about discontinuation, if possible.
- If a prisoner chooses to discontinue attendance.
- If one of the MPIs, in consultation with the relevant instructor, finds the prisoner to be so disruptive to the rest of the class that he/she has a repeated and substantive negative impact on the other participants.
- If a prisoner is released from prison unexpectedly.
- If a prisoner exhibits inappropriate behavior towards study staff.

Participants will continue with subsequent assessments if they are willing to do so. Assessment schedule and assessments used will not change.

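### The yoga-injury question is weekly in Table 4 but tied to attended classes in Table 3, so it stops when a participant stops attending and for everyone when classes end

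*Combined protocol and SAP*

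**What the plan says.** The timing of the yoga-injury question is given in several places.

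- **Protocol 7.2, Table 4:** "Weekly during first 10 weeks", with no condition on attendance. The staff action is "Follow until resolution; may result in changes to yoga instructor manual".
- **Protocol 9.1.2:** "Participants will complete a yoga homework questionnaire on a weekly basis", and then "After each homework questionnaire, we will ask participants in the yoga arm only whether they experienced any injuries as a result of yoga practice". This makes the item weekly but gives no start or end week.
- **Protocol Table 3:** the injury item and the homework questionnaire are each marked once, in the after-each-class column. Neither appears at weeks 5, 10, 14 or 18. Section 7.3 consists of a pointer to Table 3.
- **Protocol 7.4 and DSMP 3.2 (same sentence):** "Each time participants attend classes, we will inquire about injuries due to study participation".
- **Protocol 6.2.6:** "Participants will complete a brief assessment after each class that they attend". The injury item is not named here, but it and the homework questionnaire are the only entries in that column of Table 3.

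After a participant discontinues the intervention, section 8 says "Participants will continue with subsequent assessments if they are willing to do so", on an unchanged schedule. The target-outcomes table in 9.5.1 sets the safety target as no serious adverse events or injuries related to the study, and names both the SAFTEE and the injury item as sources.

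**The concern.** The two schedules agree for someone who attends every weekly class. They part when a participant stops coming. Under Table 4 and 9.1.2 the question continues. Under Table 3, 7.4 and DSMP 3.2 there is no scheduled occasion for it. Staff who follow Table 3, as 7.3 directs, will not deliver what Table 4 describes.

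An injury during class is due to be picked up that day, and a participant who returns can report on the weeks in between. The exposed case is a delayed-onset or between-class injury in someone who does not come back. Such injuries are possible because practice outside class is part of the intervention: under 5.2.1, "we will design a series of brief yoga practices that prisoners can engage in either a) on a daily basis". Section 9.1.2 also says the physical activity questionnaire was adapted to record yoga practice during follow-up, so the plan expects some practice after classes end, when no injury item is scheduled for anyone.

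Safety is a primary outcome and its target is zero related injuries. Injury could itself be a reason for stopping, although the documents do not say so. If it is, the dedicated question would be missing where it is most informative.

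**Working it through.** The plan gives no figure on this point, so there is none to reproduce. The check compares the schedules and then sizes the coverage.

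**Inputs.** 40 randomized 1:1 (DSMP 7.2), so 20 in the yoga arm. Ten weekly classes (5.1). Attendance target: 70% complete at least 6 of 10 classes (5.4, 9.5.1). Follow-up to week 18 (Table 3). Retention targets: 80% at week 10 and 70% at week 18 (9.5.1). Assumptions: the attendance target is met exactly within the yoga arm, everyone attends at least one class, and the retention targets apply to the yoga arm.

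**Intervention weeks after the last attended class.**
- Total participant-weeks: 20 × 10 = 200.
- Attending at least 6 classes: 0.70 × 20 = 14. Attending 1 to 5: 6.
- Minimum: 0, if everyone's last class is in week 10.
- Maximum: 14 × (10 − 6) + 6 × (10 − 1) = 56 + 54 = 110. This needs all 14 to stop after week 6 and the other six to stop after week 1, so it is a ceiling and not an expectation.

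**Weeks 11 to 18.** No injury item is scheduled for anyone: 20 × 8 = 160 participant-weeks.

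**What still covers those weeks.** The SAFTEE at weeks 5, 10 and 18 asks about the previous 8 to 10 weeks (7.4), so for anyone assessed the general inquiry spans the whole period. At the retention targets that is 0.80 × 20 = 16 people at week 10 and 0.70 × 20 = 14 at week 18. Reports to any staff member are also recorded. For events from any route the research assistant records perceived cause and possible relation to the study (9.1.2).

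**What a zero supports.** The exact two-sided 95% upper limit for 0 of n is 1 − 0.025^(1/n).
- n = 20: 1 − 0.025^(1/20) = 16.8%.
- n = 14 (assumed number asked the item through week 10): 1 − 0.025^(1/14) = 23.2%.

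The first limit reflects the sample size, not the schedule. The second applies to the injury item alone and ignores the SAFTEE. The comparison shows only why the number asked belongs beside the count.

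**The case against.** The strongest reply is that Table 4 is headed a summary and classes are weekly for 10 weeks, so weekly there may be shorthand for after each weekly class. Neither 7.4 nor DSMP 3.2 says that class attendance is the only occasion for the question, and 9.1.2 gives no 10-week window. That stands as a caution on wording. It does not supply a scheduled occasion for someone who has stopped attending.

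A reader might infer that injuries in dropouts go uncounted. The documents do not support that. The 9.5.1 target draws on the SAFTEE as well as the injury item, the SAFTEE continues after dropout if the participant is willing, and relatedness is recorded. What remains is an injury that a non-returner does not mention at up to three general inquiries or spontaneously.

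A reader might also infer that coverage cannot be known. It can be reconstructed, because REDCap holds dates of sessions attended and homework data (6.2.5, 10.1). Nor is the two-month follow-up of injuries promised in 7.1 and DSMP 5 without support: Table 4 requires follow-up to resolution, stop dates are recorded, and the SAFTEE is given at week 18. What is absent is a scheduled injury item that would prompt the re-check.

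On the remedy, a yoga-only question at assessment visits could threaten blinding and elicit more events in one arm. The blinding point is weak: the study research assistant is already unblinded (6.2.5) and the item is already yoga-only. The elicitation point stands in small part. The safety target is not a between-arm comparison, but any comparison of event rates should keep the two sources apart.

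**Conclusion.** The inconsistency is real and the consequence is limited. On the schedule that 7.3 points to, a yoga participant who stops attending has no further scheduled injury item, and no one has one after classes end. Any undercount of related injuries is probably small, because general inquiry and spontaneous reports can both feed the target, and its size cannot be derived from the documents. Under the stated attendance assumptions, the specific question is absent after the last attended class for 0 to 110 of 200 intervention participant-weeks, and for all 160 participant-weeks from 11 to 18. The point does not show that the trial is unsafe or that its safety count is invalid. It is a gap linked to dropout in the measurement of a primary outcome, and it is cheap to close.

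**What to change.** 1. In Table 3, add the yoga-injury item to the existing week 5, 10 and 18 assessments for all yoga participants, whether or not they attend. Word it to cover the time since it was last asked and to re-check any injury still open. Keep the after-class item.
2. Align Table 4, 7.4, 9.1.2 and DSMP 3.2 with that schedule.
3. Report the injury count with the number of yoga participants asked through week 10 and through week 18.
4. When arms are compared, report injuries elicited by the item separately from SAFTEE events.

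**Cost:** at most 20 × 3 = 60 short questions at visits already planned, with no new visits, plus the wording edits. The answers can sit in the restricted REDCap section that already holds intervention-specific data. The downside is slightly more yoga-only event elicitation, which step 4 handles. The change cannot reach participants who miss the assessments themselves; for them spontaneous report remains.
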